Does Pulmonary Rehabilitation
Improve Frailty in Chronic Lung
Disease?

NCT02512874

June 23, 2015

Introduction and Specific Aims

Frailty is defined as a decreased resistance to disability and illness. The prevalence of frailty is reported to be around 14% in elderly community populations and 17% in advanced heart and lung disease patients.(1, 2) Frailty consists of a constellation of three or more of the following characteristics: wasting, exhaustion, decreased physical activity, slowness, and weakness.(3) Patient’s with one or more characteristics are considered “pre-frail” and those with three or more are considered “frail.” Frail and pre-frail states are associated with mortality, increased falls, nursing home placements, and hospitalizations in the geriatric general population.(3-6) Frailty is also an important predictor of disease-specific outcomes in those with certain co-morbid conditions such as heart failure and osteoporosis.(3, 4, 7)

Little is known about frailty in patients with chronic lung disease. Emerging evidence by the candidate and others suggests that frailty is important for both mortality and disease-specific outcomes in lung disease patients. Preliminary evidence demonstrates the above-referenced frailty characteristics are common in chronic obstructive pulmonary disease (COPD).(8-13). In addition, this candidate has demonstrated that frailty is associated with increased mortality and hospitalization in COPD. (see preliminary data) Less is known about other chronic lung diseases and frailty. However, this candidate demonstrated that low muscle index (wasting) pretransplant is associated with worse survival and increased primary graft dysfunction following lung transplantation. (see preliminary data)

Effective strategies to improve frailty are unknown. Although patients with moderate to severe lung disease are commonly referred to pulmonary rehabilitation, it is unknown if pulmonary rehabilitation improves frailty or frailty characteristics. The main goal of pulmonary rehabilitation is to improve quality of life in patients with chronic lung disease. Although patients may increase their exercise capacity in pulmonary rehabilitation, this candidate’s preliminary data suggests that frailty persists despite pulmonary rehabilitation in some patients. Certain patient factors have been shown to be associated with successful pulmonary rehabilitation.(14) It is unknown if there are patient factors that contribute to frailty improvement following enrollment in pulmonary rehabilitation. Further study examining the benefits and limitations of pulmonary rehabilitation at effectively addressing frailty and frailty characteristics is essential to improving patient outcomes in chronic lung disease.

The long-term goal for this application is to determine effective interventions to improve frailty in patients with moderate to severe lung disease. The overall objective of the proposed research is to determine if pulmonary rehabilitation improves frailty characteristics in patients with moderate to severe lung disease. Our central hypothesis is that the current model of pulmonary rehabilitation does not optimally address frailty characteristics.

Specific Aim #1 To determine the effectiveness of pulmonary rehabilitation at improving frailty characteristics of slowness (measured gait speed), weakness (grip strength), measured activity, self-reported exhaustion, and wasting (body mass index) in a cohort of patients with moderate to severe pulmonary disease.

Specific Aim #2 To determine if patient characteristics (such as demographics, affect, and uncertainty) are associated with improvement in frailty following pulmonary rehabilitation.

The candidate is uniquely poised to perform this research. She has put together an outstanding team of experts to support her including mentorship expertise in body composition, pulmonary rehabilitation, and frailty, and support from the personnel in the Mayo Clinic Pulmonary Rehabilitation Unit. Importantly, the candidate will have access to a large pulmonary tertiary referral center population and pulmonary rehabilitation facility.

Background and significance

Frailty is defined as a decreased resistance to disability and illness. It is common (as high as 17% in advance lung disease) and associated with important patient outcomes of mortality, hospitalization, and need for nursing home.(1, 2) Frailty consists of a constellation of three or more of the following characteristics: wasting, exhaustion, decreased physical activity, slowness, and weakness.(3) Patient’s with one or more characteristics are considered “pre-frail” and those with three or more are considered “frail.” Wasting is defined as unexplained weight loss or decrease in lean body mass. It is typically measured by body composition. Exhaustion is typically measured by self-report via questionnaire. Physical activity can be self-reported through questionnaires or, more accurately, directly measured by physical activity monitors. Slowness is typically measured by gait speed (the time it takes an individual to walk 15 feet). Finally, weakness can be measured by respiratory muscle function or hand grip strength. Measures are typically adjusted for sex and height or weight and compared to expected normative values.

Little is known about frailty in patients with chronic lung disease. Emerging evidence suggests that frailty is important for both mortality and disease-specific outcomes in lung disease patients. Evidence demonstrates the above-referenced frailty characteristics are common in chronic obstructive pulmonary disease (COPD). For example, patients with COPD have been noted in separate studies to have wasting(8, 9), fatigue(10), lower physical activity(11), slower gait speed(12), or decreased strength (13). In addition, wasting has been associated with COPD mortality, and increased fatigue has been associated with increased COPD hospitalizations.(8, 10). These studies suggest the possible importance of the frailty phenotype in COPD. In addition, a mixed measure of frailty with functional and sensory deficits that found the mixed measure is associated with increased shortness of breath, health care utilization and disabilities in COPD.(15) A similar constellation of deficits was associated with an increased mortality at 12 years in patients with COPD.(16) Finally, this candidate has demonstrated that frailty is associated with increased mortality and hospitalization in COPD. (see

“Does pulmonary rehabilitation improve frailty in chronic lung disease?”

Principal Investigator (Last, First Middle): [name]

Updated: 6/23/2015

preliminary data) Less is known about other chronic lung diseases and frailty. However, this candidate demonstrated that low muscle index (wasting) pretransplant is associated with worse survival and increased primary graft dysfunction following lung transplantation. (see preliminary data) Lung transplant candidates are typically a mixed representation of several chronic lung diseases, therefore, suggesting importance of frailty beyond COPD.

In the above mentioned preliminary data, research participants underwent pulmonary rehabilitation. Despite this frailty and frailty characteristics persisted. This suggests that pulmonary rehabilitation alone may be *insufficient* to address frailty in its current form. Prior studies have attempted to identify patient factors that lead to success in pulmonary rehabilitation. (14) It is unknown if such factors will be important to successful improvement in frailty characteristics.

Proposed methodology

We propose a single-center, prospective cohort study with **Aim 1**: measurements of frailty characteristics pre- and post-pulmonary rehabilitation referral and **Aim 2**: measurements of baseline affect, uncertainty, and demographics to examine associations between patient characteristics and improvements in frailty characteristics.

Outcomes

Aim 1: Outcomes will include median change in grip strength, gait speed, physical activity, and body composition and comparison of pre and post self-reported exhaustion. In addition, prevalence of frailty and pre-frailty will be compared pre and post pulmonary rehabilitation. **Aim 2**: Associations of positive or negative affect, baseline measure of uncertainty, and demographic factors and median or percent change in frailty characteristics.

Summary of background and significance:

Frailty is common in advanced lung disease and is associated with decreased time to hospitalization, increased length of hospital stay, and increased mortality. In addition, in lung transplant patients frailty is associated with increased primary graft dysfunction and mortality. There is a knowledge gap regarding effective interventions to treat frailty and frailty characteristics. Pulmonary rehabilitation is widely available and utilized in patients with moderate to severe lung disease. Whether pulmonary rehabilitation improves frailty is unknown.

Alignment with career goals:

This proposal aligns perfectly with the candidate's goal of attaining an independent career in clinical research focusing on optimization of pretransplant risks as frailty is prevalent in pretransplant populations and associated with significant transplant risks (mortality and primary graft dysfunction). This work will serve as preliminary data for a future R01 on optimizing pre-transplant risks including frailty. Furthermore, this aligns with the candidates training goals: gaining initial experience in prospective clinical trials and physiologic and psychometric measurements and increasing competitiveness for R01 funding.

Innovation: This application is innovative because:

1. Frailty is a novel risk factor for **death and hospitalization** in moderate to severe lung disease.
2. The ability of pulmonary rehabilitation to improve frailty and frailty characteristics is unknown.

Approach:

Preliminary data

The candidate's preliminary work informs the proposed research approach. The candidate's previous work has been devoted to the study of body composition and frailty in patients with advanced lung disease. The candidate sought to determine if muscle index (a measurement of body composition and therefore wasting) correlated to important outcomes in lung transplant. We conducted a retrospective cohort study of adult lung transplant recipients at Mayo Clinic Rochester with computed tomography images of the lumbar L2-L3 level within six months of transplant. We analyzed these images using Slice-o-matic software, version 4.2 (TomoVision, Magog, Canada) to determine the skeletal muscle index (cm^2/m^2) (a measurement of body composition). Higher skeletal muscle index was beneficial with a hazard ratio (HR) of 0.89 (95% CI 0.81-0.97) and was protective against primary graft dysfunction at 72 hours. In follow-up the candidate sought to determine if frailty was important in advanced lung disease patients who do not undergo transplant. Data from the National Emphysema Treatment Trial (NETT) were therefore retrospectively analyzed. 902 patients were included. Frail patients had a worse survival with an adjusted Hazard Ratio (aHR) of 1.57; (CI) 1.08-2.29; $p=0.018$), decreased time to hospitalization aHR of 1.70 (CI 1.11-2.59; $p=0.014$) and increased hospital days (adjusted increase of 8 days; CI 5.3-10.7; $p<0.0001$). Interestingly, both our lung transplant program and the NETT trial required pulmonary rehabilitation as a condition of participation. This suggests that frailty persists in some patient despite pulmonary rehabilitation.

Based on the preliminary data, lowering the risks of frailty in patients with advanced lung disease is an unmet need and further information regarding the efficacy of pulmonary rehabilitation in treating frailty is needed.

Specific Aim #1

Participants and Criteria: Patients will be identified from the Mayo Clinic Rochester, MN Pulmonary Division. Patients who either are referred to enroll in pulmonary rehabilitation at Mayo Clinic in Rochester or who are referred for nursing education regarding pulmonary rehabilitation enrollment will be approached. **Recruitment:** A study referral reminder will be incorporated into the pulmonary rehabilitation referral and pulmonary rehabilitation nursing education referrals. **Inclusion/Exclusion criteria:** Eligible patients will be aged 18 years or older, referred for pulmonary rehabilitation, and consenting to research. **Retention strategy:** Patients will be given remuneration for completing the 3 to 6 month follow-up appointment. **Methods:** This is a single-center, prospective trial examining the effects of pulmonary rehabilitation on frailty and frailty characteristics and associations between patient characteristics and improvement in frailty characteristics. Patient will be approached for recruitment in a private setting regarding willingness to participate in the study by the principal investigator or other authorized study personnel and consented with IRB-approved consent procedure and written consent form. Patients will receive a full explanation of all procedures, risks, benefits, and alternatives and all questions will be answered. Once consented patient will undergo physiologic testing and complete questionnaires. Activity monitors will be sent with patients (including a return addressed envelope with postage) to assess one week of measured activity. At three to six months physiologic testing and activity monitor recordings will be repeated. Patients will also be asked to specify the number of completed pulmonary rehabilitation sessions. **Data: Medical Record Abstraction** Patient demographics, pulmonary diagnoses, weight, height, and pulmonary function tests will be recorded. **Physiologic Measurements and Testing: Grip strength** will be measured using a Jamar Digital Hand Held Dynamometer. Three serial measurements will be taken (using the dominant hand), averaged, and adjusted by gender and BMI using normative table. **Gait Speed** will be measured using a wireless infrared timing system. Self-selected walking speed over a distance of 15 feet will be averaged over 3 trials and then adjusted for gender and height. **Dual Energy X-ray Absorptiometry (DEXA) scan** will determine body composition (body mass, fat mass and fat-free mass) at baseline and at 3-6 months following initiation of pulmonary rehabilitation. **State-of-the-art activity monitors (Sensewear Armband, Body media, Pittsburgh,PA)** will quantify kcals burned, active and sleep time, as well as quality of sleep (baseline and 3 to 6 months following initiation of pulmonary rehabilitation).

Questionnaires

Name of questionnaire	abbrev	Purpose of questionnaire	N of items	Cronbach's alpha
Mischel Uncertainty in Illness Scale	MUIS	Uncertainty in illness measure	33	0.65-0.90
Positive Affect Negative Affect Schedule	PANAS	Positive and negative affect	20	0.84-0.90
Chronic Respiratory Questionnaire	CRQ	Disease-specific quality of life measure in lung disease	20	0.84
Short form Health Survey-26	SF-36	Exhaustion question only	1	0.82-0.95

Sample size A convenience sample of consecutive prospective consenting patients will be enrolled. This is a pilot study and therefore sample size calculations are not required. However, in order to inform our enrollment we have made the following calculations: **Change in grip strength.** A sample size of 40 per sample will have 80% power to detect a difference in means of 20%, assuming a baseline mean of 28 in women and a standard deviation of 6.3 (as reported for females age range 50-59), using a paired t-test with a 0.05 two-sided significance level.(17) However, given an estimated prevalence of frailty of 17% we would like to recruit at least 100 patients to further study frailty in a larger sample. Based on annual pulmonary rehabilitation participants at Mayo Clinic in Rochester (~150 patients), annual referrals for nursing pulmonary education (~250-300 patients), and a recruitment rate of 80% for similar studies, we feel this is realistic.

Quality Assurance / Quality Controls:

Data abstraction Spreadsheet will be standardized (for definitions and protocol) and audited by PI weekly to ensure selection criteria and protocol compliance and monthly for completion and accuracy.

Personnel training All personnel will be trained to perform the hand grip and gait speed assessments.

Analysis plan:

Patient demographic characteristics will be summarized by mean, median and standard deviation and range (continuous variables) and counts and percents (categorical variables). A two-tailed p < 0.05 will be considered statistically significant. Frail performance will be defined as a performance of <20% predicted on physiologic tests. Pre- and post- intervention

tests will be compared using Wilcoxon Signed Rank or paired t-test as appropriate. Subgroup analysis will be performed for frail patients and those completing > 6 and > 12 pulmonary rehabilitation sessions.

Budget

Primary expenses of this project include personnel time, statistical support, and participant remuneration. [name] lab will provide use of the activity monitors. [name] has necessary equipment for gait speed and grip strength determinations. Funding is provided by the Nelson Benefactor Career Development Award.

Timeline: The proposed study enrollment will be completed in the 9 months with most follow-up assessments completed in the one-year time frame.

Protection of human subjects:

Recruitment Procedures will be approved by the Mayo Institutional Review Board.

Data and materials A potential risk is loss of confidentiality. Data will be transferred into a password-protected database in a password-protected computer. Questionnaires will be coded without identifying features and will be stored in a locked cabinet. All data will be reported in composite form.

Physiologic Testing Another potential risk is discomfort, desaturation, or tachycardia during physiologic testing. Subjects will be monitored for adverse symptoms. Supplemental oxygen at the patient's usual settings will be allowed during testing. Clinical emergency response teams provide emergency medical coverage for the CRU and clinical area of Gonda 18. We estimate the risk to patient to be equivalent to daily activities.

Potential benefits Potential benefits of this study include improved knowledge of the benefits of pulmonary rehabilitation and knowledge of frailty performance characteristics.

Inclusion of women, minorities and children: Children will not be represented as frailty risks and pulmonary rehabilitation interventions differ. Our study will include women and minorities. No vulnerable group will be specifically targeted. We expect the minority population to mirror census data. Due to the demographics of the Southeast Minnesota area our targets are 2% black, 2% Asian, 4.5% Hispanic and 4.5% 'other' for an ideal target of 13% minority participation. Of course, health disparities occur in minority use of healthcare services so discrepancies may occur. In order to ensure that women and minorities will be appropriately represented and that the study population will be representative of all eligible patients, the PI will ensure that patients being considered meet criteria and no additional exclusions are applied.

Resources, environment, and personnel

Office space

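### The only Aim 1 outcome that measures frailty as a syndrome, pre/post prevalence, is insensitive, and its pre-frail part has no clear direction; a paired analysis of the 0-5 count would use the same data better

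*Combined protocol and SAP*

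**What the plan says.** All references are to the combined protocol and SAP.

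- **Outcomes, Aim 1** (under Proposed methodology) begins with the components: "Outcomes will include median change in grip strength, gait speed, physical activity, and body composition and comparison of pre and post self-reported exhaustion". It then adds that the "prevalence of frailty and pre-frailty will be compared pre and post pulmonary rehabilitation". This is the only Aim 1 outcome that treats frailty as a syndrome.
- **Introduction and Specific Aims**, and again **Background and significance**, define frailty as "three or more of the following characteristics: wasting, exhaustion, decreased physical activity, slowness, and weakness". Patients "with one or more characteristics are considered" pre-frail and "those with three or more are considered" frail. No upper limit is given for pre-frail.
- **Analysis plan** gives the pre/post tests as "Wilcoxon Signed Rank or paired t-test as appropriate", at two-sided 0.05. It names no test for paired proportions, no transition table and no analysis of the number of characteristics.
- **Analysis plan**, on cut-offs: "Frail performance will be defined as a performance of <20% predicted on physiologic tests". No cut-off is stated for self-reported exhaustion.
- **Sample size**: "given an estimated prevalence of frailty of 17% we would like to recruit at least 100 patients". The section gives no power for the prevalence comparison.

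**The concern.** The title asks whether rehabilitation improves frailty, and prevalence is the one planned comparison of frailty itself. It has three weaknesses.

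1. **Overlap.** As worded, every frail patient is also pre-frail, so a move from frail to pre-frail does not change pre-frail prevalence.
2. **No clear direction.** If pre-frail means 1-2 characteristics, a frail patient who improves raises its prevalence and a pre-frail patient who becomes robust lowers it. The reported change is the net of the two flows. Flat or rising pre-frailty is then compatible with benefit.
3. **Lost information.** Frail prevalence records only moves across three. A patient who goes from five characteristics to three, or from two to one, counts as unchanged.

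The central hypothesis is that current rehabilitation does not address frailty optimally. An insensitive comparison that comes out non-significant could be read as support for it.

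**Working it through.** **The plan's own figure.** There is none for this comparison. The 40 per sample in the Sample size section is for change in grip strength and does not bear on it. The usable inputs are 100 patients, 17% frail and two-sided 0.05.

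**Step 1: what frail prevalence needs to reach significance.** Expected frail at baseline: 0.17 x 100 = 17. The plan names no test, so an exact McNemar test is assumed. If a patients leave frailty and b < a enter it, p = 2 x [C(a+b,0) + ... + C(a+b,b)] / 2^(a+b).

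| Leave | Enter | p |
|---|---|---|
| 5 | 0 | 2/32 = 0.063 |
| 6 | 0 | 2/64 = 0.031 |
| 8 | 1 | 2 x (1+9)/512 = 0.039 |
| 10 | 2 | 2 x (1+12+66)/4096 = 0.039 |

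So at least 6 of 17 (35%) must leave with none entering, 8 of 17 (47%) if one enters, and 10 of 17 (59%) if two enter. This step assumes nothing about effect size or correlation.

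**Step 2: where moves cancel.** Take 17 frail, 50 pre-frail (1-2) and 33 robust. The 50 is assumed, since the documents give no figure; 40 or 60 gives the same p-values. Nobody worsens.

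| Moves | Frail | Pre-frail, 1-2 | One or more | Sign test on category moves |
|---|---|---|---|---|
| 8 frail to pre-frail, 8 pre-frail to robust | 17 to 9, p=0.008 | 50 to 50, p=1.0 | 67 to 59, p=0.008 | 16 of 16 better, p=0.00003 |
| 4 and 4 | 17 to 13, p=0.125 | 50 to 50, p=1.0 | 67 to 63, p=0.125 | 8 of 8 better, p=0.008 |

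Cancellation occurs only in the 1-2 column. In the second row no prevalence reaches significance, although every category change is an improvement.

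**Step 3: power by simulation.** Each of five components is a normal score, abnormal beyond a common cut-off set so that 17% have three or more. Assumed correlation is 0.2-0.4 between components and 0.6-0.8 between visits. That implies 41-54% pre-frail (1-2) at baseline. There were 1,500 replicates per scenario. Prevalences were tested by exact McNemar; the three-level category and the count by Wilcoxon signed-rank. All five components shift equally.

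| Shift, n | Frail | Pre-frail, 1-2 | One or more | Three-level | 0-5 count |
|---|---|---|---|---|---|
| 0.2 SD, 100 | 22-34% | 5-8% | 34-47% | 53-77% | 58-86% |
| 0.3 SD, 100 | 45-63% | 13-15% | 65-82% | 84-98% | 88-99% |
| 0.3 SD, 80 | 32-48% | 11-12% | 56-74% | 76-94% | 82-98% |

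With no shift, the two signed-rank analyses reject in about 5% of studies and McNemar in about 2-4%. The count's advantage is therefore not bought with excess false positives. The n=80 row allows for dropout, for which the documents give no rate.

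**Step 4: partial improvement** (n=100, 17% frail).

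| Components improving | Count | Frail prevalence |
|---|---|---|
| Two, by 0.2 SD | 17-24% | 6-7% |
| Two, by 0.3 SD | 29% | 10% |
| Three, by 0.2 SD | 35% | 13% |

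The last two rows use correlations of 0.28 between components and 0.7 between visits, with visit-to-visit variation shared across components. The range in the first row reflects whether that variation is shared or independent, plus simulation error.

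**The case against.** **Improvement is not hidden overall.** Component changes are listed first and prevalence is an addition. The stated objective concerns frailty characteristics, and no outcome is named as primary. A uniform shift would be looked for directly in the continuous measures. This stands. A reader might infer that the study would miss a real benefit; the documents do not support that. What remains is that component tests answer a question about components, and frailty itself has only the prevalence comparison.

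**Cancellation is narrow.** A reader might infer that improvement cancels out of both prevalences. It does not. Frail prevalence falls whenever a frail patient improves enough to cross three, and on the literal one-or-more definition nothing cancels. The weakness of frail prevalence is low sensitivity, which is a different fault.

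**No separate tests are stated.** The plan says only that the prevalences will be compared. Two separate McNemar tests are one natural reading, and the sentence does not rule out a three-category or ordinal comparison. This stands. It also means that the method still has to be specified.

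**The gain depends on favourable assumptions.** Equal improvement in all five components, wasting included, is generous, and Step 4 shows how fast power falls otherwise. The three-level category already gives most of the gain; the count adds about 2-10 points at n=100. Both stand. They limit the size of the gain, not its direction.

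**The count changes the question.** It weights components equally and is less familiar clinically than prevalence. This is a fair reason to keep the prevalences in the report. The count also needs a cut-off for every component, but so do the prevalences.

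**Conclusion.** The point holds in limited form. As planned, the syndrome-level comparison combines a pre-frail category that overlaps frail, or has no clear direction if read as 1-2, with a frail prevalence that needs at least 6 of about 17 patients to leave frailty and none to enter. The second result uses only the plan's figures and an exact McNemar test.

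The power ranges rest on assumptions that are not in the documents: shift sizes, correlations, a common component cut-off and, for the higher figures, improvement in all five components. Under them, the count has 58-99% power against 22-63% for frail prevalence and 5-15% for pre-frail. With two components improving by 0.2 SD, no analysis has good power (count 17-24%, frail prevalence 6-7%). The count did better than frail prevalence in every improvement scenario tried. This is a worthwhile improvement to a pilot study's analysis, not a flaw that invalidates Aim 1.

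**What to change.** Amend the Outcomes and Analysis plan sections as follows:

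1. Define the categories without overlap: robust = 0 characteristics, pre-frail = 1-2, frail = 3-5.
2. State, before the data are examined, a cut-off for each of the five components, including exhaustion.
3. Make the tested Aim 1 frailty comparison a Wilcoxon signed-rank test on each patient's pre/post 0-5 count. The plan already names this test.
4. Show the 3x3 pre/post transition table, so that moves in each direction can be seen.
5. Keep frail and pre-frail prevalence at both times with 95% CIs, as the clinically familiar summary.
6. Keep the component analyses as planned.

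The cost is wording, plus agreement on the missing cut-offs, which the prevalences need anyway. No extra patients, visits or measurements are required. The count would also give Aim 2 a patient-level measure of improvement in frailty. Any power quoted for the count should be a range with its assumptions, including the case where only some components improve.

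### With no clinical-stability condition and no dates of recent acute episodes, recovery from an episode before baseline would be counted as rehabilitation benefit wherever it occurs

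*Combined protocol and SAP*

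**What the plan says.** The Inclusion/Exclusion criteria under Specific Aim #1 read: "Eligible patients will be aged 18 years or older, referred for pulmonary rehabilitation, and consenting to research". The Sample size paragraph adds: "A convenience sample of consecutive prospective consenting patients will be enrolled". The section on inclusion of women, minorities and children says that "the PI will ensure that patients being considered meet criteria and no additional exclusions are applied".

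Baseline is tied to consent and not to the time since any acute event: "Once consented patient will undergo physiologic testing and complete questionnaires". Testing is repeated at three to six months. The Medical Record Abstraction item is: "Patient demographics, pulmonary diagnoses, weight, height, and pulmonary function tests will be recorded". None of the four questionnaires is listed as a source for recent admissions, exacerbations or steroid treatment.

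The Proposed methodology describes "measurements of frailty characteristics pre- and post-pulmonary rehabilitation referral", and the Methods state the purpose: "This is a single-center, prospective trial examining the effects of pulmonary rehabilitation on frailty and frailty characteristics". The Analysis plan compares the two time points by Wilcoxon signed rank or paired t-test. It adds subgroups for frail patients and for those with more than 6 and more than 12 sessions. It has no comparator, no adjustment, and no subgroup defined by recent acute illness.

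**The concern.** A paired before/after test without a control group attributes all average change to the intervention. It implicitly assumes that the expected change without rehabilitation is zero. A patient enrolled during or soon after an acute episode may have grip, gait, activity and exhaustion at a temporary low, and part of any later gain would have come without rehabilitation. An episode shortly before the follow-up visit would have the opposite effect and could hide a real gain.

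The eligibility rules let both situations in, and the listed data items would not show them. The frail subgroup is the most exposed, because temporary weakness, slowness, exhaustion and inactivity are among the features that define frailty.

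Aim 1 is about whether rehabilitation improves these characteristics, and the central hypothesis is that current rehabilitation does not address them optimally. Unrecognised spontaneous recovery would work against a fair test of that hypothesis.

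**Working it through.** The plan gives no figure for this point. Its only related calculation, 40 per sample for grip strength, is not used below. For the record, it is not reproduced by a paired t-test with a difference of 0.20 × 28 = 5.6: an SD of change of 6.3 needs 12 pairs. That is a separate matter.

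**Inputs from the Sample size paragraph:** grip mean 28, SD 6.3, two-sided 0.05, and a recruitment target of at least 100 (taken as 100 complete pairs).

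**Assumptions, not in the documents:** pre/post correlation r of 0.5 to 0.8; share f of patients recovering from an episode before baseline, 5% to 30%; natural recovery g of 2 or 3 grip units (7% or 11% of 28); no true rehabilitation effect; no episodes before follow-up.

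**Formulas**
- SD of change without recovery: s0 = 6.3 × √(2(1−r)). This gives 6.30 at r=0.5, 4.88 at r=0.7 and 3.98 at r=0.8.
- Spurious mean change: m = f × g.
- SD of change with recovery: s = √(s0² + f(1−f)g²).
- Chance of p<0.05: two-sided rejection probability of the paired t-test, from the noncentral t with 99 degrees of freedom and noncentrality m√100 / s. The mixture is treated as normal.

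**Worked case** (f=0.20, g=2, r=0.8): m = 0.40; s = √(3.98² + 0.16 × 4) = 4.06; standard error 0.41; noncentrality 0.98; rejection probability 16.4%.

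| Share f | Recovery g | Shift m | r=0.5 | r=0.7 | r=0.8 |
|---|---|---|---|---|---|
| 5% | 2 | 0.1 | 5.3% | 5.5% | 5.7% |
| 10% | 2 | 0.2 | 6.1% | 6.9% | 7.8% |
| 20% | 2 | 0.4 | 9.6% | 12.6% | 16.4% |
| 20% | 3 | 0.6 | 15.3% | 21.9% | 29.8% |
| 30% | 3 | 0.9 | 28.2% | 42.0% | 56.1% |

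The nominal rate is 5%. Fewer complete pairs would lower these figures.

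**Opposite direction.** If a share f₂ also loses g₂ units through an episode just before follow-up, the mean shift becomes f×g − f₂×g₂. It is zero when the two products are equal and negative when the second is larger. The table is therefore a one-sided illustration and not a forecast.

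**The case against.** A reader might infer that the protocol itself regards hospitalisation as common here, or that many patients will be referred just after an acute episode. The documents support neither. What the Background calls common is frailty. The hospitalisation results are associations: fatigue with COPD admissions, and in the Preliminary data "decreased time to hospitalization aHR of 1.70" for frail patients. A hazard ratio for later admission says nothing about recent admission at baseline.

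It is equally tempting to conclude that the study will be biased towards benefit. That cannot be established, because episodes before follow-up push the other way and neither frequency is given. At the low end of the range the error rate is barely above 5%. Even the largest shift in the table, 0.9 units, is 16% of the planned 5.6-unit difference.

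The sentence on no additional exclusions comes from a paragraph about representativeness. Broad consecutive enrolment is a defensible choice for a pilot, so the lack of exclusions is not in itself a fault.

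It can also be said that admission dates could be retrieved later from the medical record. That holds for care within the institution. It is less secure for episodes treated elsewhere at a tertiary referral centre, and a window chosen after the data are seen carries little weight.

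Finally, the root limitation is the missing comparator, and this is only one source of uncontrolled change. That is correct and limits what the fix can achieve. Pilot status lowers the stakes but does not remove the point, since the results are meant as preliminary data for a larger grant application.

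**Conclusion.** The concern holds in conditional form. The plan has no stability condition, lists no dates that would identify recent acute illness, and analyses change without a comparator. Recovery from an episode before baseline would be counted as rehabilitation benefit wherever it occurs, an episode shortly before follow-up would count against it, and the dataset as listed could show neither.

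Size and net direction are unknown. Under the assumptions above, with baseline episodes only, the chance of a significant result with no true effect runs from about 5-8% (5-10% recover 2 units), through 10-16% (20% recover 2), to 28-56% (30% recover 3). The share affected, the recovery size and the correlation are all assumed. The SD is the plan's normative value for women aged 50-59 and not an observed SD in these patients.

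**What to change.** Add to the abstraction, at both visits, the date of the last respiratory hospitalisation or exacerbation and of any systemic steroid course. Add one question to the patient about care received elsewhere. Exclude no one on this basis.

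Pre-specify a sensitivity analysis for Aim 1. Report the mean or median change with a 95% confidence interval for all patients, and again for those with no episode within a set window before either visit. Fix the window in advance, justify it against the expected recovery time, and repeat the analysis with a longer window as a check. A window shorter than the recovery period would class patients who are still recovering as stable.

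Interpret the analysis by comparing the size and direction of the two estimates. Do not require significance in both, because the smaller set could miss significance through lost power alone.

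The cost is a few extra fields, one question, one additional analysis and a wider interval in the stable set. The change exposes one source of uncontrolled change. It does not stand in for a control group or remove other regression to the mean, and the report should say so.
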